For this cluster randomized trial, we assume a Type I error rate of 0.05 and a desired power of 0.8 for the primary outcomes. Our study will include 60 microclusters (30 intervention, 30 control) with at least 8 participants in each cluster (n=480 across all clusters). We will have no fewer than 480 and can enroll up to 720. The number of participants enrolled will depend on our dynamic enrollment strategy that we've discussed already. We assume an intraclass correlation (ICC) of 0.05. For our primary outcomes (and all survey-based outcomes), we will fit a marginal model using generalized estimating equations (GEE) to estimate the effect of the intervention relative to control. Under these assumptions, we will be able to detect an intervention effect of 0.33 s.d at 80% power with 30microclusters per arm (60 total) and 8 participants per microcluster.⁹ This is a conservative estimate of power since we will adjust for the baseline value of the outcome and other covariates associated with the outcome. If we are only able to sample from 50 microclusters (25 per arm; n=400 across all clusters), we will be able to detect a moderate effect size of 0.37 s.d. at 80% power. Assuming up to 25% attrition between baseline and endline, we would still be able to detect a treatment effect of 0.31 s.d.

Statistical Analysis

Individual-level primary and secondary outcomes

For all primary and secondary outcomes drawn from our two-wave survey of 720 trial participants, we will assess differences in outcomes between the intervention and comparison groups using Generalized Estimating Equation models (GEE) that account for clustering at the study microcluster level. We will use canonical link functions for all outcomes. All models will adjust for the baseline level of the outcome, all microcluster-level characteristics used in the covariate constrained randomization (see randomization protocol),¹⁰ any individual characteristics found to be imbalanced between the intervention and control groups at baseline.

We will conduct an intention-to-treat analysis: participants that move out of (or across) study clusters, separately engage with community partner services while in the control group, or do not engage with these services while in the treatment group will all be considered exposed to their original treatment assignment.

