In addition to this "event study specification," we will also estimate a standard difference-in-differences model in which the calendar time $\times \times$ treatment interactions are replaced by intervention period $\times \times$ treatment interaction and a post-intervention period $\times \times$ treatment interaction. These two terms will capture average intervention impacts during intervention implementation and immediately thereafter, with the latter being the treatment effect of interest.

For all models, we will adjust standard errors for clustering at the study microcluster level. We will report both unadjusted and multiple-comparisons adjusted¹⁸ p-values for all outcomes.

Sub-group analyses

For our primary outcomes and survey-derived secondary outcomes, we will estimate the above GEE models separately for the following subgroups:

- Gender (persons identifying as men vs. persons identifying as women; if the sample size permits, we will also consider separate models for trans- and non-binary individuals)
- Level of education (split by the sample median years of schooling)
- Age (over 50 versus under 50)

We will assess statistical differences in treatment effects between categories within each subgroup by estimating versions of our main GEE models that fully interact all terms with the binary subgroup indicator, and assessing the standard error and 95% CI on the interaction between treatment and the subgroup indicator.

Evaluating Mechanisms

In addition to evaluating treatment effects on secondary outcomes, we will assess potential mechanisms underlying intervention effects on the primary outcomes using three *descriptive* (and exploratory) approaches.

First, we will use our survey data to examine the extent to which the non-health secondary outcomes (e.g., food security, financial security, social cohesion, stress, experiences of racism, exposure to crime, engagement with greenspaces, health care utilization) mediate the relationship between the intervention and any impacts on the primary outcomes. Specifically, we will conduct a causal mediation analysis to decompose intervention effects by each set of potential mediators. Our method will follow the strategy of Heckman et al (2013), who use an ordinary least squares based approach.¹⁹

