accessing major public benefits or who had not filed tax returns prior would be more likely to benefit from financial interventions than those already engaged with these activities. Similarly, individuals living in study clusters with relatively larger numbers of abandoned lots, fewer trees, or more abandoned homes would stand to benefit more from the environmental interventions than those who did not. Formally, we will estimate versions of our main GEE models for the primary outcomes in which we will include interactions between the treatment indicator and binary indicators for individuals participating in fewer than sample median number of public benefit programs; not filing (or had someone file on their behalf) a tax return in the previous year; being below the median of the household financial security scale; living in a microcluster below the median in terms of tree canopy; living in a microcluster that is above the median in terms of the number of abandoned lots; and living in a microcluster that is above the median in terms of the number of houses. Positive and statistically significant coefficients on these interaction terms would provide suggestive evidence that the specific intervention that would address the pre-intervention attribute in question helped drive treatment effects. For example, a positive and significant coefficient on the interaction between treatment and living in a cluster with above the median numbers of abandoned lots would suggest that abandoned lot remediation played a role in driving overall treatment effects. Interpretation of these coefficients requires knowledge of actual exposure to treatments; e.g., it would be more credible to conclude that provision of tax preparation services helped drive health outcomes if large numbers of intervention group participants reported using these services.

Primary Outcomes				
Outcome	Measure	Data Source	Type of Data	Timeframe
Overall Health Index	Composite index using method of Anderson (2008) based on three questions: rating of overall health (5-pt Likert ranging from poor to excellent); rating of how health has changed in last 6_months (better, same, worse); and number of days in the last 30 where physical or mental health precluded engagement in usual activities (self-care, work, recreation); (Oregon HIE)	Survey	Continuous (index)	Baseline, 24 months
Psychological distress	Kessler-6	Survey	Continuous (scale)	Baseline, 24 months
	Secondary Out	comes		

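### Five of the six mechanism moderators are cut at the median before the treatment interaction is tested, and no continuous version is planned; adding one is a cheap gain in information of uncertain size

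*Combined protocol and SAP*

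**What the plan says.** Section 9, Evaluating Mechanisms, third approach, adds treatment-by-moderator interactions to the GEE models for the two primary outcomes. There are six moderators. Tax filing in the previous year is naturally binary. The other five are counts or scales cut at the median:

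- benefit programs, entered as "binary indicators for individuals participating in fewer than sample median number of public benefit programs"
- the household financial security scale
- tree canopy, entered as "living in a microcluster below the median in terms of tree canopy"
- the number of abandoned lots in the microcluster
- the number of houses in the microcluster (the preceding sentence speaks of abandoned homes, so abandoned houses are presumably meant)

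The plan labels the mechanism work descriptive and exploratory. It nevertheless says that a positive and statistically significant interaction would be suggestive evidence that the matching component drove the effect.

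Section 9, Sub-group analyses, splits age at 50 and schooling at its median: "Level of education (split by the sample median years of schooling". Differences between categories are judged by "assessing the standard error and 95% CI on the interaction between treatment and the subgroup indicator". Neither place plans an interaction with the moderator left continuous.

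The only stated power is in section 9, Power Calculations: "we assume a Type I error rate of 0.05 and a desired power of 0.8 for the primary outcomes". No interaction or subgroup test has one.

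**The concern.** The rationale for the environmental moderators is worded largely as a matter of degree: more abandoned lots, fewer trees and more abandoned homes should mean more benefit. A median indicator answers a coarser question. It treats two clusters that differ by one lot across the median as different in kind, and two clusters far apart on the same side as identical.

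Interaction tests are usually weak. Three of the five cut moderators are measured on microclusters, so only 60 units inform them, roughly 15 per arm on each side of a median. Because the plan reads these coefficients by significance, information lost in the coding bears directly on which component is credited. The main risk is that a real component-specific gradient goes undetected.

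**Working it through.** **1. The plan's own power figure.** The inputs are two-sided alpha 0.05 (sidedness assumed, consistent with the 95% CI), power 0.80, "We assume an intraclass correlation (ICC) of 0.05", 30 clusters per arm and 8 participants per cluster.

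- Design effect: 1 + (8 − 1) × 0.05 = 1.35.
- Detectable effect: (1.960 + 0.842) × √(2 × 1.35 / 240) = 0.297 SD, or 0.302 with t on 58 df.

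The plan says it can "detect an intervention effect of 0.33 s.d at 80% power with 30microclusters per arm (60 total) and 8 participants per microcluster", so the figure does not reproduce. With 6 per cluster (8 less 25% attrition) the design effect is 1.25, and 2.802 × √(2 × 1.25 / 180) = 0.330. That makes the later sentence, "Assuming up to 25% attrition between baseline and endline, we would still be able to detect a treatment effect of 0.31 s.d", hard to reconcile with 0.33. This is a separate matter and does not alter the ratios below. What matters here is that the 80% belongs to a main effect.

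**2. Information kept after a cut.** If the effect changes linearly with the moderator, relative efficiency is the squared correlation between the indicator and the moderator. For a normal moderator cut at quantile p it is φ(z_p)² / [p(1 − p)]. At the median this is 0.3989² / 0.25 = 0.637, that is 2/π.

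**3. Consequence for a test that would have 80% power uncut.** Power = Φ(2.802 × √efficiency − 1.960). For the normal case: 2.802 × 0.798 − 1.960 = 0.276, and Φ(0.276) = 0.61.

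| Assumed moderator | Efficiency | Loss | Power, from 80% |
|---|---|---|---|
| Uniform | 0.75 | 25% | 68% |
| Normal | 0.637 | 36% | 61% |
| Poisson, mean 1 to 5 | 0.58–0.70 | 30–42% | 57–65% |
| Exponential | 0.48 | 52% | 49% |
| Lognormal, log-SD 1 | 0.27 | 73% | 31% |

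The starting point matters too. For a normal moderator cut at the median, 90% falls to 73% and 50% falls to 35%.

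**4. Simulation check.** This used 60 clusters of 8, ICC 0.05, a normal moderator, a linear interaction and cluster-robust errors. Power fell from 78% to 59% for an individual-level moderator and from 79% to 57% for a cluster-level one. The relative loss is much the same at both levels.

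**5. Where interaction power might really start.** With an even split and 8 per cluster, the detectable difference between halves is 2 × 0.297 = 0.59 SD for a cluster-level moderator. For an individual-level one it is 2 × 2.802 × √(2 × 0.95 / 240) = 0.50 SD. A difference of 0.33 SD would have about 34% and 46% power respectively, so 80% is a generous starting point.

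**6. Capped delivery.** Section 8.2 limits greening to 5 lots and remediation to 3 houses per cluster, so benefit may level off. Suppose the effect follows min(count, cap), and take the squared correlation of each coding with that quantity:

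- Poisson count, mean 5, cap 5: log(1+count) 0.86, raw count 0.68, median split 0.34.
- Geometric count, mean 5, cap 3: log(1+count) 0.80, raw count 0.38, median split 0.54.

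A raw linear count can therefore do worse than the split. Across the count distributions tried with plateaus at 3 or 5, log(1+count) did better than the split every time.

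**The case against.** The strongest reply is that nobody knows the shape of the effect. Delivery is capped or levelled: up to 5 lots and 5000 square feet per cluster with top-up from other lots, at most 3 houses, and roughly 10 trees. A linear gradient is therefore doubtful. If the true effect were a step at the median, the binary indicator would be the efficient coding and the linear term would be the one whose power fell from 80% to 61%. Skewed counts in 60 clusters could also give a few clusters high leverage. Some of the rationale contrasts groups, such as people not using major benefits against those already engaged. The analyses are exploratory, claim only suggestive evidence, and are to be interpreted alongside actual exposure.

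Much of this stands. It rules out raw counts as the replacement and limits the importance of the point. It does not justify the cut, because nothing in the plan suggests a step at the sample median, and log(1+count) copes better with a plateau.

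A reader might infer three stronger claims that the documents do not support:

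- **That this trial's power falls from 80% to 61%.** The 80% is for the main effect on the primary outcomes. The 61% also needs a normal moderator, a linear gradient and an even split.
- **That 61% applies to age and schooling.** The share on each side of 50 is not given, and years of schooling may tie heavily at the median. The cut at 50 also matches a band boundary used in the constrained randomization, and the separate subgroup models need categories.
- **That the loss is worst for cluster-level moderators.** Precision is lower there, but the proportional loss is nearly the same.

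**Conclusion.** The point holds as an inexpensive improvement to exploratory models. The plan cuts five moderators that could be used whole and then judges the interactions by significance. The table's losses, from a quarter to a half or more, rest on assumed distributions and a linear gradient; its power figures also assume 80% power when uncut. The documents supply none of these, so no single figure can be given for this trial. The loss concerns only the interaction terms. Tree canopy and vacancy are already adjustment covariates in the main models, and no primary or secondary treatment-effect estimate is affected.

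**What to change.** In Evaluating Mechanisms, third approach, specify that:

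- the interaction test uses the continuous moderator: the standardised scale for financial security and tree canopy, and log(1+count) for benefit programs, abandoned lots and houses
- treatment effects are reported at the 25th and 75th percentiles of each moderator, with a graphical check of shape and a note of any high-leverage clusters
- the median split is kept for display
- tax filing stays binary

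In Sub-group analyses, keep the categorical age and education results and add one continuous interaction for each.

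The cost is a change of wording in the analysis plan, plus two added interaction tests per outcome for age and schooling. The data are the same and the mechanism models keep the same number of tests. The downside is the assumption of a smooth monotone gradient: if the truth is a step at the median, the binary indicator would have been more efficient. The transformations should be fixed before outcome data are examined.

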Our two primary outcomes will focus on (1) overall health and (2) psychological distress. Our measure of overall health comes from an index based on responses to three survey questions: a self-reported rating of the participant's general health (on a 5 point Likert scale, ranging from poor to excellent); the self-reported number of days in the last 30 in which poor physical or mental health precluded engagement in the participant's usual activities; and a self-reported rating change in overall health outcomes over the last 12 months (three point scale denoting worse, same, or better). We will use the method of Anderson (2008) to create a single (standardized) index of overall health.⁷ This method uses the inverse covariance matrix of the variables to create the index and allows for missing observations.

Our measure of psychological distress is the Kessler-6 scale, a validated measure of non-specific psychological distress represented by the summed score of six questions querying the frequency of symptoms of feeling nervous, hopeless, depressed, restless, depressed, that everything was an effort, and worthless over the past 30 days.⁸ The Kessler-6 ranges from 0-24.

Secondary child health outcomes

In addition to the outcomes listed above, we plan to evaluate a series of secondary outcomes focused on child health and well-being, derived from a follow-up survey administered to participants with children ages 3 to 17 at the time of 24-month follow-up. These will include caregiver-reported child health, health care utilization, and several outcomes related to child well-being, neighborhood safety for children, and parenting, as listed in Table 2.

We will also examine additional child health outcomes for all children residing in IGNITE study clusters using secondary analysis of existing data sets. Specifically, we will assess school attendance and performance for all cluster residents using Philadelphia school district data, birth outcomes for cluster residents using Pennsylvania birth certificate data, and health care utilization outcomes for all cluster residents using electronic health record data from the Children's Hospital of Philadelphia. These outcomes are also included in Table 2. We will obtain separate approval from the Children's Hospital of Philadelphia Institutional Review Board prior to abstraction of electronic health record data for these child health outcomes.

Power Calculations

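### In the third mechanism approach, the rule that positive interactions support a component points the wrong way for the Kessler-6, which is 6 of the 12 coefficients

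*Combined protocol and SAP*

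**What the plan says.** In section 9, Evaluating Mechanisms, the third approach asks whether effects were larger in people more likely to gain from a given component. For this, "we will estimate versions of our main GEE models for the primary outcomes in which we will include interactions" between treatment and six binary indicators. The reading rule is: "Positive and statistically significant coefficients on these interaction terms would provide suggestive evidence" that the component addressing that attribute contributed to the effect. The worked example repeats the sign and names no outcome: it takes "a positive and significant coefficient on the interaction between treatment and living in a cluster with above the median numbers of abandoned lots" as a sign that lot remediation played a role. Neither sentence makes an exception by outcome.

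Section 9, Outcome Measures, fixes which outcomes these are: "Our two primary outcomes will focus on (1) overall health and (2) psychological distress". The second is the Kessler-6, described as "a validated measure of non-specific psychological distress represented by the summed score of six questions querying the frequency of symptoms", with a range of 0 to 24. Table 1 lists it as a continuous scale. Neither place says that it is reversed.

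The last of the six indicators is "living in a microcluster that is above the median in terms of the number of houses", although the rationale just before it speaks of abandoned homes.

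**The concern.** The two primary outcomes naturally run in opposite directions: one measures health, the other distress. A single sign rule cannot serve both unless one of them is rescored, and the plan does not say that it will be.

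An analyst who follows the sentence to the letter would set aside a negative Kessler-6 interaction, which is the result expected if the component works. A positive one, which points away from the component, would be recorded as support. These models are one of the plan's few means of saying which part of a bundled intervention mattered, so a reversed sign could credit the wrong part.

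**Working it through.** The plan states no figure to reproduce. The check is a count, a sign argument and a simulation that confirms the sign.

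**Inputs**
- Outcomes: 2 (section 9, Outcome Measures).
- Indicators: 6 (section 9, Evaluating Mechanisms): few public benefit programs, no tax return filed, low financial security, low tree canopy, many abandoned lots, many houses.
- Coding: each equals 1 for the group with more to gain. For the sixth this holds if it means abandoned houses, as the rationale implies.
- Link: canonical for all outcomes (section 9, Statistical Analysis). For a continuous scale I take this as a Gaussian model with identity link, so coefficients keep the direction of the raw score.
- Kessler-6 direction: the plan does not say in words that higher is worse. It follows from the score being a sum of symptom frequencies.

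**Count.** 6 indicators × 2 outcomes = 12 interaction coefficients. Of these, 6 × 1 = 6 are on the Kessler-6, and 6/12 = 50%.

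**Sign.** Let T be treatment and H the high-need indicator:

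E(Y) = b0 + b1·T + b2·H + b3·T·H

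The treatment effect is b1 when H = 0 and b1 + b3 when H = 1, so b3 is the second minus the first.
- Outcome where higher is better: more benefit at H = 1 means b1 + b3 > b1, so b3 > 0. The rule is right.
- Kessler-6: more benefit at H = 1 means a larger fall, so b1 + b3 < b1 and b3 < 0. The rule is wrong.

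A positive b3 on the Kessler-6 does not by itself mean harm. If b1 and b1 + b3 are both negative, both groups improve and the high-need group simply improves less.

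**Simulation.** The set-up was 60 clusters of 8, ICC 0.05, a cluster-level indicator, exchangeable GEE with identity link and 500 runs. The working component was assumed to give an extra benefit of 0.8 SD in the high-need group. That size is an illustration and is not in the plan.

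| Outcome | Mean b3 | Significant, positive | Significant, negative |
|---|---|---|---|
| Kessler-6 | −0.81 SD | 0/500 | 485/500 |
| Index, higher = better | +0.79 SD | 486/500 | 0/500 |

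Under the literal rule, the working component is credited on the Kessler-6 in 0/500 runs. Under a direction-of-benefit rule it is credited in 485/500 = 97%, matching the index at 486/500 = 97%. This confirms the sign. It is not a power estimate, and it does not show how likely a misreading is.

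**Related wording.** The attrition bound among the sensitivity analyses (section 9, Statistical Analysis) glosses the best outcome value as the most positive one. On the Kessler-6 the highest value is the worst. Taken literally, with worst as the opposite extreme, control dropouts would get high distress and treated dropouts low distress. That favours the intervention, whereas the plan intends a lower bound.

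**The case against.** The best defence is that *positive* here means favourable. The approach is introduced by asking who benefits more, and the attrition bound also treats *positive* as a synonym for *best*, so the authors may use the word loosely throughout. That reading is possible. But a positive coefficient, paired with statistical significance, ordinarily refers to arithmetic sign, and nothing in the protocol says otherwise. The attrition wording has the same gap, so it does not settle the matter.

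The second defence is weight. All three mechanism approaches are labelled descriptive and exploratory, the result is called only suggestive, and the plan adds that interpretation depends on actual exposure to the components. This stands, and it limits the consequence.

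Three stronger readings are tempting, and the documents do not support them:
- *Half of all mechanism testing is reversed.* The sign rule appears only in the third approach. The mediation and process-measure approaches do not use it.
- *Harm would be counted as success.* A positive Kessler-6 interaction can mean less benefit with no harm in any group.
- *One moderator was designed to measure the housing stock.* The stated rationale and the remediation component in section 8.2 both concern abandoned houses, so this is evidently a dropped word.

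Nor do the documents state that the health index is scored so that higher is better. One of its three items, days of limited activity, runs opposite to the general health rating. The orientation is natural but is an assumption here.

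**Conclusion.** The concern holds within a narrow scope. As literally worded, the rule gives the wrong reading for 6 of 12 interaction coefficients in one exploratory approach. This is a stated rule with the wrong sign for one outcome, and more than an omitted detail. The estimates themselves are unaffected; only their interpretation would be wrong, and only if the sentence is followed to the letter. The primary inference does not depend on it.

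The conclusion rests on three assumptions: the Kessler-6 is analysed unreversed, its indicators are coded as listed, and the sixth indicator means abandoned houses. The correction is worth making because the present text would not tell a later reader which sign had been specified in advance as supportive.

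**What to change.** 1. In the third mechanism approach, define support as a statistically significant interaction in the direction of benefit: negative for the Kessler-6 and positive for the health index. Alternatively, state that the Kessler-6 is reverse-scored for these models, so that positive is favourable for both. Word the abandoned-lots example to match.
2. In Outcome Measures and Table 1, state that the health index is scored so that higher is better, with the limited-activity-days item reversed before the index is formed.
3. In the attrition bound, replace the gloss on *best* with the most favourable value for that outcome, which is the lowest score for the Kessler-6.
4. As a minor correction, change the sixth indicator to the number of abandoned houses.

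The cost is a few sentences of plan wording. Data collection, sample size and the main models do not change.
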